Center for Diabetes Technology

Feasibility of a Decision Support System To Reduce Glucose Variability In Subjects with T1DM

NCT02558491
Version Date: 10-14-2016

A. Purpose/Objectives

The purpose of this study is to demonstrate the safety and feasibility of a decision support system aimed at reducing glucose variability in T1DM patients using continuous subcutaneous insulin infusion (CSII) or multiple daily injections (MDI). The system will be deployed on our portable medical application platform (DiAs) and will include the following elements:

1. An insulin pump or MDI treatment parameters optimization routine, using a month of collected CGM/insulin/meal data
2. An exercise risk warning system, capable of predicting hypoglycemia at the onset of physical activity and advising on mitigating treatments such as insulin adjustment or carbohydrate consumption
3. A smart bolus calculator based on CGM glucose measurements and insulin sensitivity estimation.

Primary Specific Aim:

To demonstrate feasibility and safety of a glucose variability-reducing decision support system, measured by non-inferiority of use of the system compared to standard SMBG-informed CSII or MDI therapy in terms of occurrence of hypoglycemia and percent time spent between 70 and 180 mg/dl as measured by blinded CGM.

Secondary Specific Aims:

To assess the effect size of using the GV advisory system compared to standard CSII or MDI therapy in terms of:

- Occurrence of hypoglycemia during and immediately after exercise
- Glycemic excursion post meals

B. Study Design Overview

Subjects: The study is intended to complete up to 20 subjects with Type 1 Diabetes Mellitus who use continuous subcutaneous insulin infusion (CSII) and up to 20 subjects with Type 1 Diabetes Mellitus who use multiple daily injections (MDI). The study will be a randomized cross-over design with a Control and Experimental admission. The order of the admissions will be randomized. It is estimated that there will be a higher than normal rate of screen failures, dropouts, or withdrawals, thus we intend to set a recruiting target of **70 subjects**.

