The Outpatient Emergency Plan will go into effect should a catastrophic event occur during the study admissions. A catastrophic event is defined as any event that requires emergency treatment by medical professionals that exceed the expected parameters of the protocol. A copy of this plan will be located at the monitoring desk. Staff will be aware of its location at all times.

In the unlikely event of a disruption in 911 phone service, the sites will contact their local non-emergency number (e.g. Charlottesville-UVA-Albemarle Emergency Communications Center can be reached via their non-emergency number [contact]). This number feeds into their main call area where 911 dispatchers are available 24/7.

Event	RN Response	Tech Response
Respiratory Arrest	1) Tell Tech to call 911 2) Begin Basic Life Support	Refer to Study Physician
Cardiac Arrest	1) Tell Tech to call 911 2) Begin Basic Life Support	Refer to Study Physician
Severe Hypoglycemic Event as defined by hypoglycemia accompanied by unconsciousness or seizure	1) Tell Tech to call 911 2) Administer glucagon IM (described in Glycemic Treatment Guidelines Appendix A-6) 3) Remove study pump	Refer to Study Physician
Severe Hyperglycemic Event as defined by β -ketone level ≥ 3.0 mmol/L	1) Discuss correction dose of insulin to administer s.c. via syringe with study M.D. 2) Encourage P.O. water intake 3) Remove study pump and start home insulin pump 4) Go to nearest medical facility for evaluation and treatment.	Refer to Study Physician

Table 3: Outpatient Emergency Plan

ENDPOINTS

We assess the risk to the subject by computing the two classical hypo and hyperglycemia risk indices LBGI and HBGI, based of the blinded CGM data, retrofitted to the SMBG point (see DelFavero et al. JDST 2015). Gaps of less than 3h will be filled using spline based interpolation. LBGI is the primary endpoint.

LBGI and HBGI are measures of glycemic risk that were developed by our groups in the late 1990s and have been shown to be predictive of increased frequency of severe hypoglycemia and increased HbA1c. Detailed formula can be found in Kovatchev et al. Diabetes Care 1998.

In addition we will capture:

- Quality of glycemic control using the percent time spent between 70mg/dl and 180mg/dl.
- Meal insulin coverage will be assessed using Area Under the glucose Curve in the postprandial state.

CLINICAL PROTOCOL

- Glucose variability will be assessed using the Risk Index (sum of LBGI and HBGI).

SUCCESS CRITERIA / GOAL

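### Glucose variability is to be assessed only by LBGI + HBGI, which mixes glucose level with spread, so a change in the index cannot be attributed to variability

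*Combined protocol and SAP*

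**What the plan says.** Variability is the system's declared target. The title is "Feasibility of a Decision Support System To Reduce Glucose Variability In Subjects with T1DM". Section A describes "a decision support system aimed at reducing glucose variability", and the primary aim opens "To demonstrate feasibility and safety of a glucose variability-reducing decision support system". Section B gives the avoidance of a CGM-induced reduction in variability as the reason for blinding the CGM to participants.

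The ENDPOINTS section plans "computing the two classical hypo and hyperglycemia risk indices LBGI and HBGI" from the retrofitted CGM trace and makes LBGI primary. It says that the two indices "have been shown to be predictive of increased frequency of severe hypoglycemia and increased HbA1c". Three further quantities are listed: "Quality of glycemic control using the percent time spent between 70mg/dl and 180mg/dl", postprandial area under the glucose curve, and, for variability, the sum: "Glucose variability will be assessed using the Risk Index (sum of LBGI and HBGI"). No SD, CV or mean glucose appears.

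The STATISTICAL ANALYSIS PLAN compares admissions by a paired t-test, with a Wilcoxon signed rank alternative for LBGI, and does not adjust for mean glucose. The SUCCESS CRITERIA / GOAL section rests on LBGI alone.

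**The concern.** By the plan's own description, LBGI and HBGI score the risk of low and of high glucose, and the pair is tied to severe hypoglycemia and HbA1c. Such scores depend on where glucose sits as well as on how much it moves. The intervention changes basal insulin, insulin sensitivity factor and carbohydrate ratio (Section B), any of which can move the mean, so a shift in level between admissions is a plausible result.

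If the level moves, the index moves too, and the plan would report that as a change in variability. The other listed endpoints do not help to separate the two, because time in range and postprandial area also depend on level. At stake is any statement that the system did, or did not, reduce variability.

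**Working it through.** **Plan's own figure.** The plan prints no value for the Risk Index, so there is none to reproduce. Its only computed statistical figure, the detectable effect size of 0.67 in Section C, does not bear on this point.

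**Inputs.** From the documents: variability is LBGI + HBGI, and no measure of spread or mean is planned. Assumed: the standard risk transform, because the formula is cited but not printed, and the glucose means, SDs and trace shapes, which are shown as ranges.

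**Formula (assumed).** f(g) = 1.509 × [(ln g)^1.084 − 5.381] and r(g) = 10 × f(g)². LBGI is the average of r over all readings, counting only those with f < 0. HBGI is the same for f > 0. Their sum is the mean of r, which is zero at about 112.5 mg/dl.

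**Step 1: flat traces (SD 0).** At 180 mg/dl, (ln 180)^1.084 = 5.964, so f = 1.509 × 0.583 = 0.879 and r = 7.73. Likewise r(70) = 7.76, r(112.5) = 0.00 and r(200) = 11.60. A trace alternating between 90 and 160 (SD 35) scores (1.72 + 4.33)/2 = 3.03. A flat trace can therefore score higher than a swinging one. These traces only show how the index behaves; they are not realistic admissions.

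**Step 2: mean moved from 180 to 150 mg/dl, SD fixed.**

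| Trace | SD | Index at 180 | Index at 150 | Fall |
|---|---|---|---|---|
| Sine, amplitude 50 | 35 | 8.52 | 4.42 | 48% |
| Sine | 50 | 9.43 | 6.26 | 34% |
| Sine, amplitude 85 | 60 | 10.38 | 8.25 | 20.5% |
| Lognormal, shifted | 40 | 8.64 | 4.68 | 45.8% |
| Lognormal, shifted | 50 | 9.14 | 5.69 | 37.7% |
| Lognormal, shifted | 60 | 9.72 | 6.93 | 28.7% |

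SD does not change in any row.

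**Step 3: U-shape.** For the lognormal at SD 50, the index is 8.39, 6.36, 5.26, 6.54, 9.14 and 12.51 at means of 110, 120, 140, 160, 180 and 200. Near the bottom it hardly moves: 5.41 at 130 against 5.69 at 150. For sine traces it is 8.63 at 140 and 8.53 at 160 with SD 60, and 3.20 at both 125 and 130 with SD 35.

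**Step 4: response to spread.** For sine traces with the mean fixed at 160, doubling SD from 35 to 70 raises the index from 5.55 to 10.67. For the lognormal, raising SD from 40 to 60 at mean 160 moves it from 5.76 to 7.50 (+1.74). A 20 mg/dl rise in mean from 160 to 180 at SD 50 adds more: 9.14 − 6.54 = 2.60.

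**Step 5: the error can run either way.** For the lognormal, SD 60 at mean 160 scores 7.50 and SD 40 at mean 180 scores 8.64. Spread has fallen by a third (CV from 60/160 = 37.5% to 40/180 = 22.2%), yet the index reports more variability.

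**Step 6: check without the formula.** Replace the index by the mean absolute distance of glucose from a fixed target. At SD 50, moving the mean from 180 to 140 cuts it from 80.3 to 47.8 (target 100), 68.6 to 42.0 (target 112.5) and 58.0 to 38.9 (target 125). The direction does not depend on the assumed transform.

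**The case against.** The Risk Index is the last of three additional quantities. No aim and no success rule uses it: the primary aim concerns hypoglycemia and time in range, the secondary aims concern exercise hypoglycemia and meal excursions, and success is judged on LBGI. The plan says openly which index it uses. The optimizer works within defined limits (Section B), so a large shift in mean is not assured, and every percentage above rests on an unprinted formula and assumed traces. All of this stands, and it limits the consequence.

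A reader might infer three stronger things, which the documents do not support.

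- That the index measures level and not variability. Step 4 shows that it responds to spread; it is a mixture.
- That it simply rises and falls with mean glucose. Step 3 shows that it is U-shaped, so some shifts nearly cancel.
- That a fall in the sum would hide a rise in hypoglycemia risk. In the sine example at SD 50 the index falls from 9.43 to 6.26 while LBGI rises from 0.00 to 0.67. But LBGI is the primary endpoint and is examined on its own, so that rise would be seen.

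A further objection is that CV is not free of level either. With SD 35.4 and the mean moved from 200 to 160, CV goes from 17.7% to 22.1%, a relative rise of 25% from level alone. That is correct, and it is why the fix asks for SD and mean glucose as well as CV.

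What the objection does not remove is that nothing in the plan separates a change in spread from a change in level, for the property that the system is named after.

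**Conclusion.** The point holds in limited form. Variability is assessed only by a sum that mixes level with spread, and no SD, CV or mean glucose is planned to separate them. With SD fixed, a mean shift from 180 to 150 mg/dl lowers the index by about 20% to 48% (sine, SD 60 to 35) or 29% to 46% (lognormal, SD 60 to 40). Shifts within roughly 125 to 160 mg/dl, depending on SD, change it little. These sizes assume the standard transform and the trace shapes shown. The direction follows from the plan's own account of the two components as risk indices for low and high glucose, and from the formula-free check.

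A reader might infer that the trial's main conclusion is undermined. It is not: the LBGI non-inferiority claim does not use the sum. Only a statement about variability is exposed.

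**What to change.** In the ENDPOINTS section, add the within-admission SD and CV of the same retrofitted CGM trace as the measures of glucose variability, compared between admissions by the planned paired test. Report mean glucose for each admission beside them, so that a change in CV can be read against any change in level. Keep LBGI + HBGI, but describe it as overall glycemic risk.

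This needs no new data, visits or participants: it is a wording change and a few summary statistics from a trace already collected. The cost is one or two more secondary comparisons.

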Visit 3: Data Collection Period. Blinded CGM data will be collected prior to the Experimental admission and analyzed by the study team to determine the optimal insulin therapy parameters that will be used during the Experimental admission. For CSII users, the insulin pump and CGM downloads will be reviewed approximately 72 hours before the Experimental admission by the study team to ensure proper collection procedures. For MDI users, data entered into the MySugr app and CGM downloads will be similarly reviewed. Subjects will also wear a 'Fitbit' to collect information activity, exercise, heart rate, and sleep. An anonymous Gmail account will be established for each subject. An app will be placed on the subject's smartphone or subject's personal laptop to facilitate weekly downloading of the Fitbit data. Additional Data Collection Periods may be requested to ensure proper data collection.

Visit 4 and 5: Research House/Hotel Admission. The Experimental and Control admission will be separated by approximately 4 weeks, 8 weeks or 12 weeks. The order of these two visits will be randomly selected. Subjects will be admitted to the research house/hotel at ~16:00-17:00 and will be discharged after approximately 48 hours.

Figure 1: Study Design

C. Sample Size and Investigational Sites

This study will be conducted at the University of Virginia Center for Diabetes Technology (CDT). Twenty subjects (N=20) with Type 1 Diabetes Mellitus who use CSII and twenty subjects (N=20) with Type 1 Diabetes Mellitus who use MDI to treat their diabetes will be needed to complete the protocol. The studies will be conducted at the CDT Research House as noted below. The study may also occur at a local hotel. Vulnerable populations (i.e. pregnant women, prisoners, etc.) will be excluded from participation. Based on our experience with similar studies, we estimate an higher than normal screen failures, dropouts, or withdrawals due to the data collection requirements and admission time restrictions; thus we intend to set a recruiting target of 70 subjects.

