- a. **Experimental Admission** – The subject will inform DiAs of the breakfast meal carbohydrates and current blood glucose level by activating the meal screen of the system. Insulin will be administered based on the new therapy regimen (basal profile, correction factor and carbohydrate ratio profiles) and according to the subject's estimate of the carbohydrate content of the meal. The subject will self-administer the DiAs-calculated meal bolus under study staff supervisor.
- b. **Control Admission** – The subject will inform DiAs of the breakfast meal carbohydrates and current blood glucose level by activating the meal screen of the system. Insulin will be administered based on the subject's regular therapy regimen (basal profile, correction factor and carbohydrate ratio profiles) and according to the subject's estimate of the carbohydrate content of the meal. The subject will self-administer the DiAs-calculated meal bolus under study staff supervisor. The subject may use a temporary basal rate in preparation for exercise per the subject's usual routine.

4. **Exercise Session:** The subject will perform a controlled exercise activity designed to maintain (HR) at ~140 bpm and starting at approximately 11:00 AM. The exercise will consist of 45 minutes of cardiovascular activities that are divided into consecutive 15 minute periods. Fingerstick BG will be performed before and after each 15 minute exercise bout and entered into DiAs via the BG entry screen. Blood glucose value must be ≥ 80 mg/dL to initiate each 15 minute exercise bout. Immediately prior and during exercise, fingerstick BG < 100 mg/dL will be treated according to the Hypoglycemia Treatment Guidelines. Subjects will wear a heart rate monitor during this exercise session.

- a. **Experimental Admission** – The subject or study staff will inform DiAs of the impending exercise session by pressing the exercise advice button. The exercise advice given by DiAs will be followed and may consist of the following:
 - i. If no risk of hypoglycemia is detected, no intervention will be recommended.
 - ii. If a mild-moderate risk of hypoglycemia is detected, DiAs will recommend a 0% temp basal rate x 1 hour for CSII users and a 12-16 gram snack for MDI users.
 - iii. If a high risk of hypoglycemia is detected, DiAs will recommend a 0% temp basal rate x 1 hour plus a 12-16 gram snack for CSII users and a 24-32 gram snack for MDI users.

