1. The subject may request to be withdrawn (withdrawal of informed consent) from the study at any time for any/no reason. The Principal Investigator, IRB-HSR, or Senior DiAs Engineer may decide to stop the trial or part of the trial at any time. In this case, the Principal Investigator will promptly inform the subject and assure appropriate therapy and follow-up, if needed. The pertinent regulatory authorities will be informed according to national regulations.
2. The subject will be stopped if time between Visit 4 and Visit 5 exceeds 100 days.
3. A subject who does not complete the protocol may be replaced or rescheduled.

4. If the subject has a positive pregnancy test, she will be stopped.
5. If the subject has a serious adverse event, he/she will be stopped.

Study procedures other than those required for subject safety would be stopped during the admissions if:

- a. The subject has a positive pregnancy test.
- b. The subject had a serious adverse event deemed related to study.
- c. Glucagon is required to treat hypoglycemia.
- d. The subject experiences a seizure.
- e. The subject experiences loss of consciousness.
- f. The subject becomes unable to eat or drink.
- g. The subject develops ketones >3.0 mmol/L.
- h. The subject develops abdominal pain, vomiting illness, fever $\geq 101.5^{\circ}\text{F}$, clinical need for acetaminophen, significant illness, or need to use epinephrine or glucocorticoids.
- i. Subjects who were not able to complete the study for reasons other than a serious adverse event (i.e. hypoglycemic seizure, etc.) will be permitted to repeat the session.

The subject may resume the study after the following problems are resolved:

1. Correction of a malfunction of the system or controller once the problem is clearly identified and the system has been repaired
2. Correction of ketones ≥ 0.6 mmol/L or BG ≥ 300 for 2 hours or more: Study may be resumed when ketones are <0.6 mmol/L and the meter glucose is between 80-250 mg/dL.
3. Loss of sensor data acquisition for more than three hours
4. If remote monitoring cannot be restored within 180 minutes, the CGM receiver will be unblinded and study staff will monitor it at least hourly. Values will remain blinded to the subject by covering the display.

Reason Study Stopped	Repeat Session?
Equipment Failure or similarly related issues that invalidate study data	Can repeat session
Hyperglycemic Events that did not result in Serious Adverse Event	Can repeat session

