Hypoglycemic Events that did not result in Serious Adverse Event	Can repeat session
PI initiated discontinuation of study due to patient or equipment concerns	Can repeat session
Serious or Unanticipated Adverse Event deemed related to the study	Unable to repeat session

Table 1: Repeat Session Table

SAFETY MONITORING

Adverse Events, Unanticipated Problems, Protocol Violations and Data Breaches

Reporting of events are noted below:

Type of Event	To whom will it be reported:	Time Frame for Reporting	How reported?
Any internal event resulting in death that is deemed DEFINITELY related to (caused by) study participation (Note: An internal event is one that occurs in a subject enrolled in a UVa protocol.)	IRB-HSR	Within 24 hours	IRB Online and phone call www.irb.virginia.edu/
Internal, Serious, Unexpected adverse event	IRB-HSR	Within 7 calendar days from the time the study team received knowledge of the event. Timeline includes submission of signed hardcopy of AE form.	IRB Online www.irb.virginia.edu/
For Device Studies: Unanticipated adverse device effects (internal)	IRB-HSR	Within 10 day calendar days of the study team receiving knowledge of the event	IRB Online www.irb.virginia.edu/
Unanticipated Problems that are not adverse events or protocol violations This would include a Data Breach.	IRB-HSR	Within 10 day calendar days of the study team receiving knowledge of the event	IRB Online www.irb.virginia.edu/

CLINICAL PROTOCOL

Protocol Violations/Noncompliance The IRB-HSR only requires that MAJOR violation be reported, unless otherwise required by the sponsor OR Enrollment Exceptions	IRB-HSR	Within 7 calendar days from the time the study team received knowledge of the event.	Unanticipated Problem report form. http://www.virginia.edu/vprgs/irb/HSR_docs/Forms/Reporting_Requirements-Unanticipated_Problems.doc
Data Breach	IRB-HSR	Within 7 calendar days from the time the study team received knowledge of the event.	Protocol Violation, Noncompliance and Enrollment Exception Reporting Form http://www.virginia.edu/vprgs/irb/hsr_forms.html Go to 3 rd bullet from the bottom

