As a general rule, a session will be considered useful for data analysis if the subject completes more than 80% of the active study protocol. Subjects completing less than 80% of the protocol may be rescheduled.

Safety and feasibility will mean that using our system, subjects will not increase either their risk of hypoglycemia as measured by LBGI (non-inferiority claim)

STATISTICAL ANALYSIS PLAN

All variables are continuous and though bounded by 0 unlikely to be close to their lower bound, therefore we will compare the control and experimental admissions using a paired Student t-test for equality of mean. Nonetheless, LBGI may be very low in some subjects during the control admission. If such effect is observed in more than 5 subjects, LBGI will be studied using the Wilcoxon signed rank test.

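### The 80% completion rule, combined with repeats and replacement after a hypoglycaemia stop, lets the primary outcome decide which sessions enter the LBGI comparison; a true increase would be understated, by an unknown and probably small amount

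*Combined protocol and SAP*

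**What the plan says.** - **Inclusion.** Success Criteria / Goal gives, as a general rule, that "a session will be considered useful for data analysis if the subject completes more than 80% of the active study protocol". It adds: "Subjects completing less than 80% of the protocol may be rescheduled". How the 80% is counted is not defined.
- **Endpoint and claim.** The Endpoints section makes LBGI primary. Safety and feasibility mean not increasing the "risk of hypoglycemia as measured by LBGI (non-inferiority claim"). No margin is given.
- **Stops.** The events that end study procedures during an admission include "Glucagon is required to treat hypoglycemia", seizure and loss of consciousness.
- **Repeats and replacement.** Table 1 (Repeat Session Table) has a row for "Hypoglycemic Events that did not result in Serious Adverse Event" and permits a repeat. The criteria for stopping an individual subject add: "A subject who does not complete the protocol may be replaced or rescheduled". Section D also allows an admission to be repeated if it was suspended or inadequate.
- **Analysis.** The Statistical Analysis Plan names a paired t-test for equality of means, or a Wilcoxon signed rank test if LBGI is very low in more than five subjects. It does not say whether CGM data from a stopped session are kept or which attempt is analysed after a repeat, and it plans no sensitivity analysis.

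**The concern.** LBGI measures the risk of low glucose. If low glucose ends a session early, and early-ended sessions are left out and replaced by a repeat or another subject, the sessions with the worst values of the primary outcome are the ones most likely to disappear. Whether a session is analysed then depends on the outcome being measured. If the system raises hypoglycaemia, more Experimental than Control sessions are lost in this way, and the remaining comparison looks more favourable than the full one. For a claim of being no worse on hypoglycaemia risk, that is the direction that needs protection.

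The undefined 80% line adds to this. The study deliberately challenges subjects with exercise, and whether a stop during the second challenge counts as inside or outside the rule depends on a counting choice that could be made after the data are seen.

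**Working it through.** **1. The plan's own figure.** Section C gives a detectable effect size of 0.67 at 0.8 power. A paired t-test with n = 20 and two-sided 0.05 (alpha and sidedness assumed) gives 0.660, with power 0.811 at 0.67. The figure reproduces, so n = 20 and this test are used below.

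**2. Where 80% falls.** Section B: "Subjects will be admitted to the research house/hotel at ~16:00-17:00 and will be discharged after approximately 48 hours". Day 2 exercise is "designed to maintain (HR) at ~140 bpm and starting at approximately 11:00 AM"; Day 3 exercise starts at about 10:00.

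- By time: 0.80 × 48 = 38.4 h, which is 06:24 on Day 3 for a 16:00 start and 07:24 for a 17:00 start.
- Day 2 exercise: 19/48 = 39.6% or 18/48 = 37.5%. A stop there fails the rule.
- Day 3 exercise: 42/48 = 87.5% or 41/48 = 85.4%. A stop there passes.
- By scheduled items (6 meals + 2 exercise sessions = 8): a stop during Day 3 exercise comes after 5 meals and 1 exercise session, 6/8 = 75%. The same stop now fails.

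**3. Direction and size.** The documents give no stop rate, LBGI spread or margin, so every input here is assumed. Session LBGI is log-normal, Control median 1, log-SD 0.5 between and 0.5 within subjects. Experimental LBGI is h times the Control distribution. Logit(stop probability) = a + s × ln(LBGI). A repeat is used as it stands. One million pairs per setting.

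For h = 1.5 the true mean increase is 0.5 × exp((0.25 + 0.25)/2) = 0.642.

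| Control stop rate | s | Experimental stop rate | Shrinkage, repeat used | Shrinkage, pair dropped or replaced | Subjects stopped in either admission | P(no stop in 20) |
|---|---|---|---|---|---|---|
| 1% | 2 | 2.1% | 3.5% | 5.4% | 3.1% | 0.535 |
| 1% | 3 | 2.7% | 6.6% | 9.7% | 3.6% | 0.480 |
| 2% | 2 | 4.1% | 5.7% | 9.2% | 5.9% | 0.294 |
| 2% | 3 | 5.1% | 9.5% | 15.0% | 6.8% | 0.247 |

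P(no stop) is (1 − share stopped)^20, using unrounded shares.

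- Equal arms (h = 1): mean differences within 0.002 of zero.
- System helps (h = 0.75): the benefit is understated by 1.9-5.8% with repeats and 2.9-8.4% with dropped pairs.
- In absolute terms at h = 1.5, the bias runs from 0.642 × 0.035 = 0.02 to 0.642 × 0.150 = 0.10. The standard error for 20 subjects is about 0.30, so the bias is at most about a third of one standard error.

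**4. Effect on the test and on the bound.** At h = 1.5, the power of the paired t-test to detect harm is 0.54-0.55 with all sessions and 0.54-0.56 after selection. At h = 1.25 it is 0.20 against 0.20-0.21. Selection removes spread about as fast as it removes the mean. The upper confidence bound does fall, by about 4-10% with repeats at h = 1.5.

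**5. Sensitivity to the assumptions.** Another assumed set (between-subject log-SD 0.6, Control stop rates 1-5%, stopping either fully determined by LBGI or loosely linked to it) retains 58-94% of a true 50% increase, that is, 6-42% shrinkage. The direction is stable; the size is not.

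**6. What truncated first attempts would do.** This was simulated with a stand-in low-glucose score, because the documents do not print the LBGI formula. With a true ratio of 1.5 and Control stop rates of 1-2%, first attempts cut at the stop overstated the increase by 1.6-5.9%. The over-80% analysis with repeats understated it by 4.4-13.5%. The SD of the paired differences rose from 2.31 to 2.69 (2.69/2.31 = 1.16) at the least and from 2.28 to 3.35 (3.35/2.28 = 1.47) at the most.

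**The case against.** **Stops should be rare.** The explicit hypoglycaemia stops are glucagon, seizure and loss of consciousness. Ordinary lows are treated and the session goes on. The stopping rules cite a hypoglycaemic seizure as an example of a serious adverse event, and a related serious event cannot be repeated, so the repeat route is mainly for non-serious, glucagon-type stops. This stands and limits the size. Replacement remains open in every case.

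**The wording is permissive.** A reader might infer that the plan orders stopped sessions to be discarded. It does not: the rule is general, rescheduling is optional, and discarding is an inference from reading the sections together. But no passage keeps those data either, so the choice is left to case-by-case judgement.

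**The named test is not made easier to pass.** A reader might infer that the rule biases the trial's test towards non-inferiority or inflates a false-claim rate. The documents do not support that. The t-test's power to detect harm is practically unchanged, and without a margin no non-inferiority error rate can be computed. What remains is a smaller estimate and a lower upper bound.

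**Stops are not hidden.** The investigator reviews early withdrawals and each subject's data. That is true, but the review does not feed into the LBGI result.

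**Conclusion.** The point holds in a limited form. The plan's rules, read together, allow inclusion in the primary comparison to depend on the primary outcome, and the 80% line is ambiguous at the Day 3 exercise session. Confidence is high on that and on the direction: a true LBGI increase, and its upper bound, would be too small; equal arms give no mean bias; a true benefit is understated.

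Confidence is not high on size. About 3-10% shrinkage with repeats (5-15% if pairs are dropped or replaced) rests wholly on an assumed 1.5-fold increase, Control stop rates of 1-2% and an assumed link between LBGI and stopping. In a group of 20 there may well be no stop and so no effect. A changed test result is not shown, and any gain for the safety claim depends on a margin that the SAP does not state. This is a modest point, worth acting on because the remedy is cheap.

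The sections on adverse events differ on which hypoglycaemic events are recorded as adverse events. That is a separate matter, and those passages must be reconciled.

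**What to change.** Change the SAP only; the clinical stopping and repeat rules stay as they are.

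1. Keep the over-80% analysis and prespecify a sensitivity analysis of LBGI on the first attempt at each admission. Use all blinded CGM up to the stop and include sessions stopped for glycaemic reasons before 80%. Report both estimates with confidence intervals, and discuss any disagreement when the safety conclusion is stated. Agreement should not be a formal gate: without a margin it cannot be applied, and the truncated analysis is too noisy to carry it.
2. In that sensitivity analysis, let a repeat or replacement stand in for a first attempt only when that attempt was lost for a non-glycaemic reason, such as equipment failure.
3. Beside the LBGI result, tabulate stopped, repeated, replaced and unpaired sessions by admission type and reason, whether or not the stop was recorded as an adverse event.
4. Define how 80% is measured (hours, or scheduled meals and exercise sessions), and which attempt enters the over-80% analysis when a session stopped after 80% is repeated.

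Cost: some SAP wording, one extra analysis and one table, from CGM data collected up to the stop. The downside is that truncated sessions cover fewer meals and exercise bouts and give a noisier LBGI that may be biased in either direction, which is why the added analysis is a sensitivity analysis only.
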